**Synopsis**

Product provided by:	BiogenIdec Inc.
Investigational Product/ Drug Product:	Interferon beta-1a (IFN $\beta$ -1a)
Title of the Study:	A Pilot Study to Evaluate the Safety and Efficacy of IFN $\beta$ -1a in the Treatment of Patients Presenting with Ebola Virus Illness.
Development phase:	I/II
Sponsor-Investigator:	[name] [name]
Collaborator:	[name]
Planned Study Period:	January/February 2015 to April/May 2015
Primary Objective:	To evaluate the effectiveness of IFN $\beta$ -1a on viremia in peripheral blood
Primary Endpoint:	Viral load reduction/clearance: Reduction and/or clearance in copies/mL of viral RNA from day 1 to day 14 and, if applicable, 30 days after the last dose
Secondary Objectives:	To evaluate the safety of IFN $\beta$ -1a in the treatment of Ebola virus disease
Secondary Endpoints	
Occurrence and severity of adverse event; time to onset from the initial dose, duration (number of days), severity, and seriousness of solicited and non-solicited injection site reactions and systemic adverse events occurring up to 7 days after the last injection. Occurrence, nature, time to onset from the initial dose, duration, severity, relationship to injection of SAEs throughout the trial, and up to 30 days post-treatment.
 
The frequency of clinically important (moderate or severe) adverse events will be compared between the IFN <math>\beta</math>-1a treatment group and the group receiving usual standard of care.
 
The frequency of serious adverse events will be compared between the groups.

Tertiary Objectives	
To evaluate the effect of IFN <math>\beta</math>-1a therapy on preventing Ebola virus disease progression and/or on resolution of disease.
 
To assess effects on disease symptoms and survival.

Tertiary Endpoints	
Clinical improvement will be evaluated by comparing the following parameters between the groups:
 
Days in treatment centre
 
Days of symptom manifestation: hemorrhage (as IFN <math>\beta</math>-1a may cause fever, myalgia, sore throat, headache, nausea, vomiting, and diarrhea similar to that associated with ebola virus infection, these adverse events will be recorded but not used in the analysis of efficacy).

	Death – all causes for study duration
Methodology/Trial Design:	This is a Phase I/II, interventional trial designed to assess the safety and trends in clinical course of Ebola virus disease in patients $\geq 18$ and $< 70$ years of age treated with either IFN $\beta$ -1a and usual supportive care, or usual supportive care only. It is associated with appropriate monitoring of therapy.
Planned Sample Size:	Pilot: 30-50
Treatment and Specimen Collection Schedules and Duration of Follow-up:	Subcutaneous injection of IFN $\beta$ -1a daily for up to 10 days. Up to 11 blood samples will be drawn on days 1-10 and one month after discharge from the treatment centre. Subjects will be followed for the duration of their stay in the treatment centre. From first patient enrolment to last patient last visit, it is expected that the study will last 4 months.
Investigational Product:	Recombinant IFN $\beta$ -1a; an injectable sterile suspension with licensed IFN- $\beta$ provided in single use syringes
Form:	Sterile, clear, colorless preservative-free liquid, single-use syringe
Composition:	Each 0.5 mL of 60 microgram (mcg)/mL of IFN $\beta$ -1a in a pre-filled glass syringe contains 30 mcg of IFN $\beta$ -1a, 0.79 mg of sodium acetate trihydrate USP; 0.25 mg of glacial acetic acid USP; 15.8 mg of arginine hydrochloride USP; and 0.025 mg Polysorbate 20 in water for injection, USP to a pH of about 4.8.
Route:	Subcutaneous (sc) injection - undiluted
Lot Number:	V32482
Inclusion Criteria:	
Only potential patients fulfilling all of the following criteria are eligible for trial enrolment:
 
 
1. Able to provide informed consent. Substitute decision maker may provide informed consent in cases where the patient is ill and unable to provide informed consent.
 
2. Aged <math>\geq 18</math> years and <math>< 70</math> years of age on the day of inclusion.
 
3. In the treatment centre.
 
4. Suspect, probable or confirmed Ebola virus infection as per case definitions.
 
5. Symptom onset <math>< 4</math> days.
 
6. Able to comply with trial procedures.
 
 
The treating physician is responsible for recommending and for initiating therapy with IFN <math>\beta</math>-1a through the Special Access/Compassionate Release Program.

Exclusion Criteria:	A potential subject fulfilling any of the following criteria is to be

	
excluded from the randomized controlled trial enrolment:
 
 
1. Known hypersensitivity to interferon beta preparations
 
2. Pregnancy (the use of IFN <math>\beta</math>-1a is associated with abortifacient effects in rhesus monkeys and may cause miscarriage in humans)
 
3. Chronic liver disease with synthetic dysfunction and/or decompensation (ascites, hepatic encephalopathy, history of bleeding oesophageal or gastric varices)
 
4. Moderate to severe congestive heart failure (CHF) - grade III or IV left ventricular function
 
5. Previous history of serious psychiatric illness (e.g. psychosis, suicide ideation and/or attempt, depression requiring hospitalization)*
 
6. History of severe or active autoimmune disease (systemic lupus erythematosus, thyroiditis, vasculitis).
 
 
* These precautions will be reconsidered on a case-by-case basis for patients who are ill to weigh the risks and benefits of IFN <math>\beta</math>-1a therapy in the presence of these underlying conditions.
 
The exclusion criteria can be reviewed by the treating physician to assess the potential risks of therapy through the Special Access/Compassionate Release Program.

Precautions and temporary contraindications
	
The following should be considered precautions or temporary contraindications since these conditions can be exacerbated by administration of IFN <math>\beta</math>-1a. However, if they can be corrected and/or controlled prior to and during administration of IFN <math>\beta</math>-1a, they will not result in exclusion of the potential participant:
 
 
1. Thrombocytopenia (platelets <25,000/<math>\mu</math>L or bleeding disorder contraindicating SC injection)
 
2. Neutropenia (Absolute neutrophil count <1000/<math>\mu</math>L)
 
3. Anemia (hemoglobin <70g/L)
 
4. Uncontrolled seizures
 
5. Moderate to severe uncontrolled hypertension
 
6. Clinical gout
 
 
These precautions should be reviewed by the treating physician to assess the potential risks of therapy through the Special Access/Compassionate Release Program.


Statistical Methods and Analyses
	
Endpoints will be described and compared between baseline and day 10, for the treatment group using cross-tabulation tables and Fisher's Exact test for categorical variables, t-test for normally distributed continuous variables, and Wilcoxon non-parametric test for non-normally distributed continuous or ordinal variables. Data collected will be compared with a retrospective analysis of age-matched Ebola-infected individuals who presented with similar symptoms (and viral loads) and who did not receive IFN <math>\beta</math>-1a.

	
Safety variables such as fever will be considered in three different formats:
 

1. As ordinal, representing various levels of severity of the AE. For instance, fever will be described as “none”, “mild”, “moderate” or “severe”.

2. As binary, considering only the presence vs. the absence of the AE.

3. As binary, considering the most serious expression of the AE. For instance by grouping “moderate” and “severe” together.

 
Separate analyses for time periods of 0-3, 4-7 and 8-10 days will be conducted. For each of these time periods the most severe report of the AE for each participant will be counted.
 
Adverse Events and Serious Adverse Events will be considered in two ways: presence of any event and presence of any event related to the treatment.
 
Viral clearance and symptom endpoints will be analyzed as binary variables for detection (presence) or non-detection (absence) as well as continuous variables where applicable (e.g.; quantitative RT-PCR measurements).

--	---

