### **2.3.2 Procedures to Minimize Risks**

Alcohol swabbing of the skin prior to venipuncture and IFN  $\beta$ -1a injection, and use of sterile disposable needles and syringes will minimize the risk of infection. Applying pressure over needle puncture sites to minimize bruising should also be carried out. Exclusion of patients who have previously experienced a severe allergic reaction to IFN  $\beta$  preparations, and since participants will probably remain in the treatment centres for the duration of treatment, trained personnel will be available in case for allergic reactions post-injection.

For the first ten (10) ebola-infected subjects to receive IFN  $\beta$ -1a, a staggered administration schedule will be used to minimize the effect of any unforeseen serious adverse events in this patient population. The second patient will not be administered IFN  $\beta$ -1a until the first subject has received five (5) doses. Likewise, the third subject will not be administered IFN  $\beta$ -1a until the second subject has received 5 doses. If, in the opinion of the treating physician and the Special Access Program in Conakry, Guinea, no unforeseen serious adverse events are observed five (5) days after the tenth subject has received IFN  $\beta$ -1a, more than one of the remaining

subjects enrolled/to be enrolled in the study may receive their first dose of IFN  $\beta$ -1a on the same day.

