### 6.3 Treatment Schedule

IFN  $\beta$ -1a will be obtained from BiogenIdec Inc., Cambridge, MA 02142, USA. The dosage will be as follows: 6 million IU SC  $\times$  10 days. Administration should follow the product monograph, and will generally be done by the patient's nurse while in the treatment centre.

The IFN  $\beta$ -1a dose may be decreased if there are problems with tolerance by 3 million IU (15  $\mu$ g) to 3 million IU. Once it is well tolerated, the dose may remain the same or may be re-increased by 3 million IU to a maximum of 6 million IU/30  $\mu$ g per day. Dose adjustments are under the treating physician responsibility.

The duration of treatment may be shorter than 10 days in cases where the patient recovers more rapidly, with a minimum of 7 days therapy. The decision to stop IFN  $\beta$ -1a therapy in such cases will be made by the patient's treating physician. In general, patients are expected to discontinue treatment upon discharge from the treatment centre or about 48 hours prior to discharge for observation of deterioration of treatment. Most patients are expected to be admitted at least 7 days due to the nature of the illness. If any patient needs to discontinue prior to day 7 of therapy, the rationale will be documented on a case-by-case basis.

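### The synopsis compares days in the treatment centre as clinical improvement, but in the IFN group alone discharge is partly tied to the treatment course

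*Protocol*

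**What the plan says.** The tertiary endpoints in the protocol synopsis open with "Clinical improvement will be evaluated by comparing the following parameters between the groups", and the first parameter is "Days in treatment centre". Section 9.3, where the body defines the tertiary endpoints, lists fever, other symptoms and death. It does not list length of stay.

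The treatment course is described in three places:

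- **Synopsis, treatment schedule:** injections are given "daily for up to 10 days".
- **Section 6.3:** "The duration of treatment may be shorter than 10 days in cases where the patient recovers more rapidly, with a minimum of 7 days therapy". Administration "will generally be done by the patient's nurse while in the treatment centre". Treatment is expected to stop either on discharge or "about 48 hours prior to discharge for observation".
- **Section 2.3.2:** trained staff will be on hand for allergic reactions "since participants will probably remain in the treatment centres for the duration of treatment".

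The comparison group (Sections 5 and 6.1) consists of patients with Ebola virus disease who did not receive IFN β-1a. Their data are collected retrospectively and matched on age, sex, days since symptom onset and, if available, viral load. They have no course to complete and no observation period after a drug.

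**The concern.** Days in the centre can stand for speed of recovery only if both groups leave under the same rule. Here a treated patient who recovers early generally still has a minimum course to complete, and may also be watched for about two days off drug. An untreated patient with the same illness can leave on recovery. The difference between groups then contains a part produced by giving the drug, whether or not it works.

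The protocol accepts this principle elsewhere. The same part of the synopsis drops fever, myalgia, nausea and similar symptoms from the efficacy analysis because IFN β-1a can cause them. Length of stay is also affected by giving IFN β-1a, yet it is kept.

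The distortion from the course can only lengthen IFN stays, and it falls on the fastest recoverers, where an antiviral benefit would be looked for. Section 16 makes a trend toward efficacy against standard of care, if one can be seen in a small sample, a factor in extending the trial to 100 participants. A misleading comparison of stay could enter that judgement.

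**Working it through.** The protocol gives no length-of-stay figure, effect size, power or significance level for this endpoint, so there is no planned figure to reproduce. What follows is an illustration of how large the effect could be.

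**From the documents**

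- Minimum course of 7 days (Section 6.3).
- Optional observation of about 48 hours (Section 6.3), so minimum course plus observation is 7 + 2 = 9 days.
- 30 to 50 treated patients (Section 5).
- t-test or Wilcoxon test for continuous endpoints (Section 10.2).
- Fatality of 57–90% (Section 1.1).

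**Assumed**

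- IFN β-1a is inert.
- The natural survivor stay T is lognormal with median m of 8, 10, 12 or 15 days and log-SD s = 0.4.
- The first dose is given on admission.
- A treated survivor stays max(T, f), where f is the earliest discharge that the course allows. An untreated survivor stays T.

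**Formula for the added mean stay among survivors**

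E[max(T, f)] − E[T] = f·Φ(a) − m·exp(s²/2)·Φ(a − s), with a = ln(f/m)/s. Φ(a) is the share of patients whose natural stay is shorter than f.

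**Example, m = 10 and f = 9**

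- a = ln(0.9)/0.4 = −0.263, so Φ(a) = 0.396 and Φ(a − 0.4) = 0.2535.
- The mean natural stay is 10 × exp(0.08) = 10.83 days.
- Added stay = 9 × 0.396 − 10.83 × 0.2535 = 0.82 days.

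**Results**

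| Natural median (days) | Share with natural stay under 7 days | Added days, f = 7 | Added days, f = 9 |
|---|---|---|---|
| 8 | 37% | 0.58 | 1.57 |
| 10 | 19% | 0.24 | 0.82 |
| 12 | 9% | 0.10 | 0.41 |
| 15 | 3% | 0.03 | 0.15 |

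**Effect on a test.** I used 1,000 simulated trials per setting, 40 patients per group (assumed, within 30–50) and a two-sided Wilcoxon test at 0.05 (assumed). Deaths were set at 0% or at 50% in both groups, with a median death on day 5. With an inert drug the test declares a difference this often:

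| Natural median (days) | f = 7, no deaths | f = 7, 50% deaths | f = 9, no deaths | f = 9, 50% deaths |
|---|---|---|---|---|
| 8 | 18% | 7% | 85% | 23% |
| 10 | 5% | 6% | 25% | 9% |
| 12 | 5% | 6% | 6% | 6% |
| 15 | 5% | 5% | 5% | 5% |

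The columns without deaths are a limiting case. At the stated fatality, and with an inert drug, survivors would number between 30 × 0.10 = 3 and 50 × 0.43 = 21.5, or about 21. The 50% columns are closer but still use a fatality below the stated range. Fewer survivors lower the chance of a false result; they do not change the added days per survivor.

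**The case against.** The strongest reply is that no sentence in the protocol keeps patients in until the course ends. Section 6.3 largely lets discharge end treatment, and it allows stopping before day 7 with a documented reason. Section 6.2 foresees patients leaving before day 10. The remark in Section 2.3.2 is a prediction about where patients will be, made to explain staffing, and is not a discharge rule. Section 6.3 also anticipates that illness alone will keep most patients in for a week or longer, so a 7-day minimum would seldom bind. The endpoint is tertiary, in a feasibility pilot, and missing from the section that defines endpoints.

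Most of this stands, and it limits the size of the point. It does not remove the asymmetry. If therapy generally lasts at least 7 days and stops at or before discharge, discharge generally follows day 7 of therapy in treated patients, and untreated patients have no counterpart.

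A reader might infer something stronger: that an inert drug would look as if it delays recovery because patients are held for 10 days plus 48 hours. The documents do not support that. Ten days is a ceiling, the 48 hours is one of two alternatives, and a 12-day minimum stay appears nowhere and conflicts with the early discharges foreseen in Section 6.2.

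Nor is the net bias of the whole comparison known to run against IFN β-1a. Early death also shortens stay, and a retrospective matched comparison can carry other biases in either direction. Only the part caused by the course has a fixed sign.

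**Conclusion.** The point holds in a limited form. In the IFN group only, discharge is partly tied to the treatment course, so days in the centre is not a clean measure of recovery. An inert drug could appear to lengthen stay by an unknown amount:

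- **Minimum course alone:** about 0.2 days or less if the natural median is 10 days or more, with a false-positive rate close to the nominal 5%; about 0.6 days if the median is 8.
- **Minimum course with the 48-hour observation routinely added:** about 0.8 to 1.6 days among survivors for natural medians of 10 and 8 days.

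These sizes rest on an assumed lognormal stay and on how the centres apply Section 6.3. The document settles neither. The disagreement between the synopsis and Section 9.3 is certain and does not depend on the size of the bias. Given the tertiary rank and the pilot setting, this is a cheap improvement and not a threat to the trial's main conclusions.

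**What to change.** Remove days in treatment centre from the between-group efficacy endpoints in the synopsis, which brings it into line with Section 9.3 on this item. Report stay descriptively by group, separately for survivors and for patients who die, with a note that stay in IFN patients is partly set by the course. Reconcile the synopsis with Sections 6.2, 6.3 and 9.3, so that the text states consistently how the end of treatment and discharge relate and which tertiary endpoints apply. This requires no change to dosing, treatment duration or discharge practice.

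The cost is a change of wording and one fewer tertiary comparison. I would not add a fit-for-discharge date as a substitute. Comparator charts are retrospective, with acknowledged gaps, and may not hold such a date. In IFN patients it would be a judgement made with knowledge of treatment.

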### **5. Study Design**

This study is single-arm clinical trial with a pre- and post- study design. The study will include patients who are admitted with EBOV infection to a treatment centre. If a patient meets the inclusion criteria and gives informed consent (or informed consent is given by a substitute decision maker who is responsible for the patient due to the patient's illness), the patient will be enrolled into the study i.e. the first 30-50 eligible patients will be enrolled. Patients who receive IFN  $\beta$ -1a will be treated through the Special Access/Compassionate Release Program (consent to treatment through their treating physician) administered in Conakry, Guinea. This part of the study will collect data retrospectively, including results from research testing of (residual/to be discarded) blood samples. The study team can make available the systematic data collection forms to the treating physician to help in monitoring of adverse events and effect of therapy, enabling more specific reporting to the Special Access Program administered in Conakry, Guinea by the treating physician for patients receiving IFN  $\beta$ -1a.

As noted above, retrospective data collection will include patients with EBOV disease who do not participate in this clinical trial. Data from IFN  $\beta$ -1a-treated patients will be matched with data from patients who did not receive IFN  $\beta$ -1a, based on age, sex, estimated days post-onset of symptoms, and viral load (if available). This data collection is similar to that proposed in this protocol. Also, this protocol proposes to test blood collected clinically (residual or to be discarded) for comparisons between the groups in this interventional study.

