## 10.2 Statistical analyses and methods

Demographics, and underlying conditions will be described by means and standard deviation for continuous variables, by median and interquartile range for ordinal or count variables, and by frequencies and percentages for categorical variables. Endpoints will be described and compared between treatment and usual standard of care groups using cross-tabulation tables and Fisher's Exact test for categorical variables, t-test for normally distributed continuous variables and Wilcoxon non-parametric test for non-normally distributed continuous or ordinal variables.

Safety variables such as fever will be considered in three different formats:

1. As ordinal, representing various levels of severity of the symptom. For instance, fever will be described as "none", "mild", "moderate", or "severe".
2. As binary, considering only the presence vs. the absence of the symptom.
3. As binary, considering the most serious expression of the symptom. For instance by grouping "moderate" and "severe" together.

Separate analyses for time periods of 0-3, 4-7, and 8-10 days will be conducted. For each of these time periods the most severe report of the AE for each participant will be counted.

Adverse Events and Serious Adverse Events will be considered in two ways: presence of any event and presence of any event related to the treatment.

Symptoms will be assessed as a repeated measure using GEE modelling.

Survival will be analyzed using a Kaplan-Meier curve and Cox-proportional hazard modeling with 2 week and 1 month survival rates determined.

Viral clearance will be analyzed as binary variables for detection (presence) or non-detection (absence) as well as continuous variables where applicable (e.g. quantitative RT-PCR measurements).

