#### **16. Analysis of Final Data**

The initial results of the pilot trial will determine if it should be extended (extension to 100 participants per this protocol) and whether a larger multicenter study will be appropriate. Determining factors will be safety and, if possible with the small sample size, a trend toward efficacy when compared to the standard of care regimen. In addition, the effect of the treatment regimen on viral detection will be examined.

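### The synopsis ties its tests to baseline versus day 10 within the IFN group, Section 10.2 ties the same tests to IFN versus usual care, and neither contrast is named as the main one for viral load

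*Protocol*

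**What the plan says.** **Which comparison carries the tests.** The Synopsis (Statistical Methods and Analyses) states: "Endpoints will be described and compared between baseline and day 10, for the treatment group using cross-tabulation tables". Fisher's exact test, the t-test and Wilcoxon follow in the same sentence. The next sentence adds a second comparison, with no test attached: "Data collected will be compared with a retrospective analysis of age-matched Ebola-infected individuals who presented with similar symptoms". Section 10.2 uses the same list of tests for a different contrast: "Endpoints will be described and compared between treatment and usual standard of care groups using cross-tabulation tables". It does not mention baseline versus day 10.

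**What the design is.** Section 5 opens: "This study is single-arm clinical trial with a pre- and post- study design". It then describes matching IFN-treated patients to untreated ones on age, sex, time since symptom onset and, where it exists, viral load. Under its pre- and post-trial heading it names untreated Ebola patients as the comparison group. The Synopsis describes patients who receive either IFN "and usual supportive care, or usual supportive care only", and its exclusion criteria list who is to be "excluded from the randomized controlled trial enrolment".

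**How the result is used.** Section 16 bases extension on safety and, if the small sample allows, "a trend toward efficacy when compared to the standard of care regimen". It adds that the effect on viral detection will also be examined, without naming a contrast.

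**The concern.** The primary endpoint in Section 9.1 is clearance or reduction of viral RNA from day 1 to day 10. The Synopsis and Section 10.2 apply one list of tests to two different hypotheses about it. One is that viral load changes over time in treated patients. The other is that treated and untreated patients differ. An analyst could follow either text and claim to have kept to the protocol.

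The choice matters because the two tests behave differently when the drug does nothing. Section 1.1 puts Ebola virus fatality at 57-90%, so 10-43% of patients survive, and Section 1.2 says that no specific treatment is approved. If some patients clear virus unaided, a before-and-after test registers that as change. The pre/post label in Section 5 invites a reader to take the change as efficacy.

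Fisher's exact test also assumes independent groups, and baseline and day 10 are two measurements on the same patients.

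**Working it through.** The protocol states no alpha, power or effect size, and Section 10.1 justifies 30-50 patients by feasibility. There is therefore no figure of the plan's own to reproduce. The calculation below shows how the Synopsis test behaves when the drug is inert.

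**Inputs**
- n = 30 and 50 (Section 10.1).
- Survivors at 57% fatality (Section 1.1): 30 × 0.43 = 12.9, taken as 13; 50 × 0.43 = 21.5, taken as 21.
- Assumed, because the protocol is silent: two-sided 0.05; all patients PCR-positive at baseline; a share p of those sampled at day 10 clearing naturally, over a range.

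**Step 1: clearances needed.** With 0 of n clear at baseline and x of n at day 10, the two-sided Fisher p-value is 2·C(n,x)/C(2n,x).
- n=30: x=5 gives 0.052; x=6 gives 0.024.
- n=50: x=5 gives 0.056; x=6 gives 0.027.
- n=13: x=4 gives 0.096; x=5 gives 0.039.

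So 6 of 30, 6 of 50 or 5 of 13 is enough.

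**Step 2: chance of reaching that number.** This is P(X ≥ threshold) for X ~ Binomial(n, p).

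| Natural clearance p | n=13 | n=21 | n=30 | n=50 |
|---|---|---|---|---|
| 0% | 0 | 0 | 0 | 0 |
| 10% | 0.6% | 5% | 7% | 38% |
| 20% | 10% | 41% | 57% | 95% |
| 30% | 35% | 80% | 92% | 99.9% |
| 50% | 87% | 99.6% | about 100% | about 100% |

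The rate p applies to the patients sampled, so the columns are not like for like. Twenty per cent of 30 is 6 patients; the same 6 among 13 survivors would be 6/13 = 46%. At 90% fatality only 3 to 5 survivors remain: the test cannot reject with 3, and with 5 it rejects 19% of the time at p=50% and 74% at p=80%.

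**Step 3: does pairing cure it?** Exact McNemar gives p = 2 × 0.5^x when all changes go one way: 0.0625 at x=5 and 0.031 at x=6. Its threshold is also 6, so its rates at n=30 and n=50 equal those in the table. At n=13 it gives 3% at p=20% and 71% at p=50%. Pairing makes the test valid as a test of change, but does not remove natural clearance. The continuous form has the same problem. A paired t-test with an assumed natural fall of 1 log10 and an SD of change of 1 to 2 rejects in 75% to about 100% of trials at n=30, and in 38% to 91% at n=13.

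**Step 4: the Section 10.2 contrast.** Fisher's exact test between two equal, comparable groups with the same natural clearance rejects in 1.4% to 3.5% of trials (13 to 50 per group, p from 20% to 80%). That holds only if the groups are comparable, which retrospective controls do not guarantee.

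**The case against.** The strongest reply is that the protocol does plan a comparator. The Synopsis sentence after the disputed one compares treated patients with matched untreated ones. Section 5 names untreated patients as the comparison group, and Sections 9.2 and 9.3 compare between groups. That stands. A reader might infer that the Synopsis relies on the pre/post comparison alone, and the text does not support this. What it shows is that the named tests sit on the pre/post contrast and that the comparison with untreated patients has none.

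A second reply concerns the decision. A reader might infer that a spurious pre/post p-value would trigger the extension. Section 16 does not say so: its determining factors are safety and a trend against standard of care. The risk is confined to how the viral-load result is reported and read.

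A third reply is that the calculation rests on unstated quantities. That also stands. Eligibility admits suspect and probable cases, who may be PCR-negative at baseline, and Sections 5 and 6.5 expect missing data.

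Two further readings go beyond the text. The t-test and Wilcoxon are not said to be unpaired, and both have paired forms; only Fisher's test is unpaired by construction. Section 5 speaks of matching but gives no ratio and does not say that matching is patient by patient, so it cannot be assumed that the group comparison is paired.

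None of this removes the conflict between the Synopsis and Section 10.2. It is not detail that a separate analysis plan would merely fill in, because the protocol already fixes two different contrasts.

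**Conclusion.** The conflict is real and should be fixed. The same tests are assigned to a within-group contrast in one place and a between-group contrast in another, neither is named as primary for viral load, and the three design descriptions cannot all be true.

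If the Synopsis sentence is followed and its result read as efficacy, the false-positive rate with an inert drug can be far above 5%. Under the stated assumptions with complete data it is 7% (n=30) or 38% (n=50) at 10% natural clearance, 57% or 95% at 20%, and 92% or 99.9% at 30%. With 13 sampled survivors it is about 10% at 20% clearance and 87% at 50%. It is zero for the binary endpoint if nobody clears naturally. It would therefore be too strong to say that the test is almost certain to be significant whatever the drug does: that depends on a clearance rate the protocol does not give. What does not depend on that rate is that the contrast has no control for natural course, and that Fisher's exact test is invalid for repeated measurements on the same patients.

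**What to change.** - In both the Synopsis and Section 10.2, name the comparison with matched untreated patients as the main viral-load contrast. This agrees with the comparison group in Section 5 and the criterion in Section 16.
- State beside it that the controls are retrospective and non-randomised, so confounding remains and can itself produce a false difference.
- Report the baseline-to-day-10 change within the IFN group descriptively, with a confidence interval and no efficacy p-value. Any test of it must be paired.
- State how the matching is done, and use an analysis that respects the matching actually carried out.
- Describe the design throughout as single-arm with a matched non-randomised comparator. Delete 'randomized' from the Synopsis exclusion criteria and the either/or wording from its trial design entry.

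The cost is wording changes, a little more analysis work, and a result likely to look less favourable than a pre/post p-value. No additional patients are needed.
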